7.4 Sample size and power calculations

A total of 24 subjects will be enrolled with 1:1 randomization to either tamoxifen or placebo. Should a randomized patient drop-out before 24 weeks of treatment, that patient will be replaced to ensure at least 12 patients complete 24 weeks of treatment in each arm. For the primary study endpoint of TAPSE, we will have 71% and 88% power, respectively, to detect a drop from 1.80 cm or 1.85 cm at baseline to 1.60 cm (the risk boundary for RV dysfunction) using an SD for the within-subject difference of 0.25 cm.

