Study Design	Single-center, randomized, double-blind, placebo-controlled Phase II study of 24 subjects with PAH. Eligible subjects will be randomized to treatment with a 1:1 ratio using a permuted-block randomization algorithm. All subjects will also be treated with background standard of care therapy at the discretion of their PAH care physician.
Number of patients	24 patients; 12 will be allocated to tamoxifen and 12 will be allocated to placebo.
Duration of Therapy	24 weeks
Study Drug	
Tamoxifen: 20 mg
 
Tamoxifen is an oral selective estrogen receptor modulator (SERM).

Study Observations	
 • Subjects will be evaluated in person at baseline, 12 weeks, and 24 weeks. • Subjects will have telephone follow-up at 1, 3, 6, 9, 15, 18, 21 weeks. • Laboratory tests including a complete blood count, routine chemistry tests (creatinine and electrolytes), liver function tests, coagulation studies, calcium, and • BNP levels and other biomarkers will be assessed at baseline and 24 months. • Subjects will undergo a six minute walk test at baseline, 12, and 24 weeks.

	
 Subjects will have a transthoracic echocardiogram at baseline, 12 and 24 weeks. Estrogen receptor (ESR) density, as determined by ¹⁸FES PET, will be assessed at baseline and 24 weeks. Quality of life will be assessed by SF36 and emPHasis-10 at baseline, 12 and 24 weeks.
Safety Assessments	Analyses will be performed for all patients having received at least one dose of study drug. General safety endpoints such as adverse events will be reported according to FDA guidelines.
Sample Size and Power	A total of 24 subjects will be enrolled with 1:1 randomization to either tamoxifen or placebo. Should a randomized patient drop-out before 24 weeks of treatment, that patient will be replaced to ensure at least 12 patients complete 24 weeks of treatment in each arm. For the primary study endpoint of TAPSE, we will have 71% and 88% power, respectively, to detect a drop from 1.80 cm or 1.85 cm at baseline to 1.60 cm (the risk boundary for RV dysfunction) using an SD for the within-subject difference of 0.25 cm.

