1.1 Definition and characterization of PAH

Pulmonary arterial hypertension (PAH) is defined by a mean pulmonary artery pressure > 25 mm Hg, a pulmonary vascular resistance > 3 WU, and a normal pulmonary capillary wedge pressure in the absence of other etiology of pulmonary hypertension²⁴. While the histopathologic findings demonstrate endothelial cell expansion, smooth muscle hypertrophy, and *in situ* thrombosis within the smallest pulmonary arteries, the disease mechanism is unknown^{25, 26}. Current therapies promote vasodilation of residually functional vessels, but are not curative. Survival from death or lung transplantation remains low, approximately 60% at three years, and 50% at five years.

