3.1 Recruitment

3.1.1 Identification and screening process

Subjects will be identified by the medical staff who care for patients with PAH at Vanderbilt University Medical Center. We expect to pre-screen 60 subjects per year over 4 years, totaling ~200 patients with PAH pre-screened over 4 years. Potentially eligible subjects will then undergo the screening process. This number, approximately 60 total subjects who undergo telephone screening, will be informed about the study to determine if they have an interest in enrolling. After the initial screening, the subject will provide informed consent before any study procedures are performed.

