3.3 Randomization

The Research Pharmacy at Vanderbilt University Medical Center will prepare numbered drug kits containing 12 week supplies of tamoxifen or placebo and these will be used sequentially. Tamoxifen or Placebo Distribution will occur at baseline and week 12. Subjects will be randomized to treatment with a 1:1 ratio (tamoxifen : placebo) using a permuted-block randomization algorithm.

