3.4 Maintenance of treatment randomization code and procedures for breaking the code

The treatment randomization code will be maintained by the research pharmacist at Vanderbilt University Medical Center. The code is to be broken only if knowledge of treatment assignment for that subject is required to initiate appropriate therapy of an adverse event (AE) or if the safety of the subject is at serious risk if treatment is continued without knowledge of the treatment assignment. The decision to unmask will be made by the PI ([name]), [name], and the Chair (or co-Chair) of the Data Safety Monitoring Board.

Unblinding may only occur for emergency purposes which would affect clinical care. Investigators should note that the occurrence of a serious adverse event or progressive disease should not routinely precipitate the immediate unblinding of the label. Even with unblinding, the number of unblinded individuals should be limited to only those who need to know the treatment identity (e.g., only the local physician caring for the subject).

Chapter 4. Treatments

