4.5 Treatment masking

All study personnel and subjects will be masked for the duration of the study until the last subject completes follow-up assessments. The VUMC Investigational Drug Pharmacist, the unblinded statistical analyst, and the DSMB will be unmasked; the Investigational Drug Pharmacist will supply the DSMB and the identified biostatistician with the drug/placebo identifier. This review will occur only in a closed meeting.

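### Does the replacement rule in 7.4 need a stated maximum and a named by-arm count of completers before the trial can be run?

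*Combined protocol and SAP*

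**What the plan says.** Section 7.4, repeated in the tabular abstract, sets enrolment at 24 with 1:1 randomization. For a patient who leaves before 24 weeks of treatment it adds: "that patient will be replaced to ensure at least 12 patients complete 24 weeks of treatment in each arm". The abstract's row on the number of patients gives a fixed total: "24 patients; 12 will be allocated to tamoxifen and 12 will be allocated to placebo". Section 7.1 and the narrative abstract also describe a study of 24.

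Section 3.3 has the pharmacy prepare numbered kits "containing 12 week supplies of tamoxifen or placebo and these will be used sequentially", from a permuted-block list of unstated block size. Section 3.4 says "The treatment randomization code will be maintained by the research pharmacist at Vanderbilt University Medical Center". Section 4.5 says "All study personnel and subjects will be masked for the duration of the study until the last subject completes follow-up assessments". It exempts the pharmacist, the unblinded analyst and the DSMB, and says of the review for which the code is supplied: "This review will occur only in a closed meeting".

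Three items are absent: a maximum number randomized, the way a replacement is assigned (next kit or same-arm kit), and the role that tracks completers by arm. No dropout rate is assumed anywhere. Section 7.3.1 puts all randomized subjects in the intention-to-treat analysis. Sections 5.3 and 7.3.3 ask subjects who stop treatment to keep attending assessments.

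**The concern.** The target is per arm, but kits are used in list order. If a replacement takes the next kit, it falls in the dropout's arm only by chance, so one replacement per dropout cannot guarantee 12 and 12. Enrolment would have to go on until both arms reach 12, and the masked staff who enrol cannot see when that happens.

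The size of the trial would then be open. Section 3.1.1 foresees "approximately 60 total subjects who undergo telephone screening". Out of 60, 24 randomized needs a yield of 24/60 = 40%, 32 needs 32/60 = 53%, and 39 needs 39/60 = 65%. At stake would be the recruitment forecast, the number of people exposed, and whether the fixed totals of 24 can stand beside a rule that adds subjects.

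**Working it through.** **1. The plan's own power figure.** Inputs from 7.4: change 0.20 or 0.25 cm, SD of the within-subject difference 0.25 cm, 12 per arm; from 7.3.1, two-sided 0.05. Standardized effects are 0.20/0.25 = 0.8 and 0.25/0.25 = 1.0. A one-sample (paired) t-test with n = 12, by the noncentral t, gives 71.4% and 88.3%, matching the stated 71% and 88%. The stated power is therefore for change within one arm. That is a separate matter; here it serves as one yardstick for a shortfall.

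**2. What dropout rate do the documents support?** None is stated. Section 1.1 gives a rough anchor: "Survival from death or lung transplantation remains low, approximately 60% at three years", and the same sentence adds 50% at five years. With 24 weeks = 0.46 year and constant hazard:
- from three years: 1 − 0.60^(0.46/3) = 7.5%
- from five years: 1 − 0.50^(0.46/5) = 6.2%
- from years 3 to 5 alone: 1 − (0.50/0.60)^(0.46/2) = 4.1%

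The anchor is thus about 4% to 7.5%. It counts only death and transplant. Excluding Functional Class IV may lower it, and other reasons for stopping raise it. Rates of 10% to 20% are assumptions.

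**3. Is 24 a minimum?** Yes, under any replacement method: 24 suffices only if nobody drops out, with probability (1 − p)^24 = 29%, 8%, 2% and 0.5% at p = 5, 10, 15 and 20%. This follows from the replacement rule itself, not from the sequential kits.

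**4. Next-kit replacement.** Simulated with blocks of 4 (assumed), equal independent dropout in both arms, status known before the next kit is issued, and replacements able to drop out too.

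| Dropout | An arm below 12, one-for-one | Share of these short by exactly one | Mean N, one-for-one | Mean N until both reach 12 | Extra subjects | 95th percentile of N, both reach 12 |
|---|---|---|---|---|---|---|
| 5% | 38% | 92% | 25.3 | 25.9 | 0.6 | 29 |
| 10% | 53% | 85% | 26.7 | 27.7 | 1.0 | 32 |
| 15% | 61% | 78% | 28.2 | 29.6 | 1.4 | 35 |
| 20% | 65% | 72% | 30.0 | 31.7 | 1.7 | 38–39 |

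Blocks of 2 to 8 move the shortfall column by only a few points. At the lower anchor rates of 4.1% and 6.2%, the mean until both arms reach 12 is 25.5 and 26.3, with 95th percentiles of 28 and 30.

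**5. Same-arm replacement.** Each dropout is replaced in the same arm, and so is any replacement who drops out. Both arms end at 12, the shortfall is zero, and masked staff need only the number of dropouts, which they can see.

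**6. What does a shortfall cost?** For the planned between-arm rank-sum test with 24 completers (SD of change 0.25 cm in each arm and normal data assumed), splits of 12/12, 13/11 and 14/10 all give about 43% power at 0.20 cm and 61% at 0.25 cm. For the within-arm test of step 1, an arm with 11 has 66.8% and 84.8%, that is 71.4 − 66.8 = 4.6 and 88.3 − 84.8 = 3.5 points less. The other arm then has 13 and gains: 75.4% and 91.1%.

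**The case for a change.** The strongest case for a change is that the rule promises a per-arm result that the described mechanism does not deliver. No same-arm kit is described; sequential use is. Even with same-arm kits, someone unmasked must issue them, and the number randomized still has no ceiling. Those who approve and fund the trial have reason to want that number, since every extra subject is exposed to study drug and has PET scans at baseline and week 24. Writing it down would take a short paragraph and one figure.

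The omissions are real, and so is the inconsistency between the fixed totals of 24 and a rule that can add to them. What does not stand is the step from omission to defect. Section 3.3 describes kit use in general and does not address replacements. Under 3.3, 3.4 and 4.5 the pharmacy prepares the kits and its pharmacist holds the code and is unmasked. Nothing there bars the pharmacist from issuing a same-arm kit or telling staff only whether enrolment continues; the closed-meeting sentence governs a review of unmasked material. Section 8.1 refers to a manual of procedures, where such steps may sit.

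A ceiling also has a price. With a maximum of 32 and next-kit assignment, the target of 12 per arm would be missed in about 3, 15 and 36% of trials at 10, 15 and 20% dropout. Whether to guarantee completers or bound the total is the sponsor's trade-off.

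**Conclusion.** No change to the plan is needed. The protocol leaves out a maximum, the assignment method for replacements and the holder of the by-arm count, but these are logistics that roles already unmasked can handle without telling study staff any allocation. The analysis does not depend on them: every randomized subject stays in the intention-to-treat set, enrolment stops on completion counts and not on TAPSE, and subjects who stop treatment but attend week 24 still contribute data.

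At worst, with next-kit assignment one-for-one, an arm usually ends one completer short, with no material loss for the between-arm test. Meeting the target in both arms then takes on average 0.6 to 1.7 further subjects at 5% to 20% dropout. These sizes rest on assumed dropout rates, an assumed block size and equal dropout in the two arms; the documents' own survival figures point to about 4% to 7.5% over 24 weeks for death or transplant alone. Confidence is moderate, because the intended assignment method is not stated. The fixed totals of 24 are best read as 24 plus replacements.

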2.1 Objective

To evaluate the change (Week 0 to 24) in tricuspid annular plane systolic excursion (TAPSE), determined by transthoracic echocardiography (TTE), in tamoxifen versus placebo.

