6.1 Assessments of efficacy

Primary

To evaluate the change (Week 0 to 24) in tricuspid annular plane systolic excursion (TAPSE), determined by transthoracic echocardiography (TTE), in tamoxifen vs. placebo.

Secondary

There are several secondary objectives of this study. They include:

- To evaluate the change (Week 0 to 24) in other echocardiographic metrics of right ventricular function determined by TTE in tamoxifen vs. placebo.
- To evaluate the effect of tamoxifen vs. placebo on TAPSE at Week 12 by TTE.
- To evaluate the effect of tamoxifen vs. placebo on other echocardiographic metrics of right ventricular function at Week 12 by TTE.
- To evaluate the effect of tamoxifen vs. placebo on 6MWD at Week 12 and Week 24.
- To evaluate the effect of tamoxifen vs. placebo on the SF36 and emPHasis-10 at Week 12 and 24.
- To evaluate the effect of tamoxifen vs. placebo on plasma BNP level at Week 24.
- To evaluate the effect of tamoxifen vs. placebo on metabolism-related biomarkers at Week 24.
- To evaluate the change (Week 0 to 24) in sex hormone, and sex hormone metabolite, levels in the urine and plasma (Week 0 to 24) in tamoxifen vs. placebo.
- To evaluate the change (Week 0 to 24) in estrogen receptor (ESR) density, as determined by ¹⁸FES PET, in tamoxifen vs. placebo.
- To evaluate the safety and side effects associated with tamoxifen administration in subjects with PAH.

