7.3 Statistical procedures

7.3.1 Data analysis

The intent-to-treat analysis will include all randomized subjects. Hypothesis testing will use two-sided $\alpha = 0.05$ without correction for multiplicity.

The primary and secondary endpoints are described in Chapter 6.

Continuous endpoints will be analyzed using the Wilcoxon Rank Sum test to assess between treatment arms difference and using the signed rank test for within-group change from baseline. For binary endpoints, Fischer's exact test will be used to assess between treatment arms difference.

For the primary endpoint, TAPSE, an exploratory analysis using mixed effects model will be conducted to assess the time trend and treatment effect (tamoxifen vs placebo). The mixed effects models will have a random subject effect and we will use an autoregressive model of order 1 (AR1) or other plausible covariance structures for the error covariance. In addition, the association between baseline (pre-tamoxifen or placebo) lung ESR density and response to treatment quantified by TAPSE and 6MWT distance will also be evaluated using the mixed effects models. These analyses will be of particular interest since they will help us *a priori* to identify patients who will be most likely responders to tamoxifen in the next-phase studies should this proof-of-concept study be a success.

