7.5 Interim monitoring guidelines

We have not planned for formal interim analyses for efficacy and therefore there are no stopping rules for efficacy for this trial. This is a 'proof of concept', early Phase II trial which will be useful in supporting future studies of the intervention even if null.

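### The 71% and 88% power quoted for the primary endpoint belongs to a before-after test in one arm of 12; the plan gives no power for tamoxifen versus placebo

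*Combined protocol and SAP*

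**What the plan says.** The primary objective is the Week 0 to 24 change in TAPSE, "determined by transthoracic echocardiography (TTE), in tamoxifen versus placebo" (section 2.1). Section 6.1 repeats it as the primary efficacy assessment: "determined by transthoracic echocardiography (TTE), in tamoxifen vs. placebo".

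On the test, section 7.3.1 says: "Continuous endpoints will be analyzed using the Wilcoxon Rank Sum test to assess between treatment arms difference". It adds a signed-rank test for change within each group and sets a two-sided 0.05 level with no multiplicity correction.

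The only power statement is in section 7.4 and is repeated in the abstract. It is tied to the primary endpoint, TAPSE, and the effect is expressed as a fall from baseline: "we will have 71% and 88% power, respectively, to detect a drop from 1.80 cm or 1.85 cm at baseline to 1.60 cm", "using an SD for the within-subject difference of 0.25 cm". It names no test, no expected change on placebo and no difference between arms. The sample size is 24, randomized 1:1, with dropouts replaced so that at least 12 per arm complete treatment.

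**The concern.** The effect in section 7.4 is a change from baseline, and its SD is that of a within-subject difference. Those are the inputs to a one-sample (paired) calculation. A between-arm calculation needs a difference in change between tamoxifen and placebo and the sampling variance of two arm means. With equal arms and equal SDs, the variance of the difference between two arm means is twice that of one arm's mean. The same centimetre effect is therefore harder to detect between arms than within one arm.

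If the quoted power belongs to the one-arm question, the randomized primary comparison has no stated power, and this is the only justification of the sample size for the primary endpoint. Section 7.5 describes the study as an "early Phase II trial which will be useful in supporting future studies of the intervention even if null", and one secondary aim in section 2.2 is to size a larger study. A reader of a null primary result could take it as coming from a test with 71% to 88% power. Because section 7.3.1 plans both between-arm and within-arm tests, a one-arm power figure also invites reliance on the within-arm result, which cannot separate a drug effect from change over time.

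**Working it through.** **Inputs from the documents**
- Effect: 1.80 − 1.60 = 0.20 cm and 1.85 − 1.60 = 0.25 cm (section 7.4)
- SD of within-subject change: 0.25 cm (section 7.4)
- Two-sided 0.05 (section 7.3.1)
- 12 per arm, 24 in total (abstract, section 7.4)

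**Step 1. Reproduce the stated power.** Paired t-test, n = 12, 11 degrees of freedom, critical value 2.201, noncentrality = effect ÷ (SD/√n).
- 0.20 cm: 0.20 ÷ (0.25/√12) = 2.77, power 71.4%
- 0.25 cm: 0.25 ÷ (0.25/√12) = 3.46, power 88.3%

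Both stated figures are matched. None of the alternatives tried matches the pair:

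| Calculation | Power at 0.20 / 0.25 cm |
|---|---|
| Paired t, all 24 pooled | 96.3% / 99.7% |
| Paired t, n = 11 | 66.8% / 84.8% |
| Paired t, n = 13 | 75.4% / 91.1% |
| Paired t, n = 12, one-sided | 82.9% / 94.5% |
| Paired, normal approximation, n = 12 | 79.1% / 93.4% |
| Exact signed-rank, n = 12 | 66.7% / 85.0% |
| Two-sample t, 12 per arm | 46.6% / 64.9% |
| Two-sample t, 24 per arm | 77.4% / 92.4% |

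**Step 2. Power for the primary comparison.** This needs two assumptions that the documents do not supply: (a) the change SD is the same in both arms; (b) the between-arm difference in change equals the stated drop, which would be so if placebo does not change. Changes are also taken as normally distributed.

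Standard error of the difference = 0.25 × √(2/12) = 0.102 cm. Noncentrality = 0.20/0.102 = 1.96 and 0.25/0.102 = 2.45. On 22 degrees of freedom (critical value 2.074), two-sample t power is 46.6% and 64.9%.

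For the planned test, the exact two-sided rank-sum with 12 versus 12 rejects when U ≤ 37 or U ≥ 107, with true size 0.0449. Simulation with 200,000 runs per case gives about 43% and 61%.

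**Step 3. Sensitivity to the assumed SD, 12 per arm**

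| Change SD | Rank-sum, 0.20 / 0.25 cm | Two-sample t, 0.20 / 0.25 cm |
|---|---|---|
| 0.20 cm | 61% / 80% | 65% / 83% |
| 0.25 cm | 43% / 61% | 47% / 65% |
| 0.30 cm | 31% / 46% | 35% / 50% |

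For a two-sample t-test to reach 71% and 88%, the change SD would have to be about 0.19 cm.

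**Step 4. What the design can detect at SD 0.25 cm**
- Difference detectable with 80% power: about 0.31 cm by rank-sum (79% at 0.310 cm, 80% at 0.315 cm); 0.30 cm by t-test
- 95% CI half-width for the difference in mean change: 2.074 × 0.102 = 0.21 cm
- Patients per arm for 71% and 88% between arms: about 21 by t-test, about 22 by rank-sum

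**The case against.** The strongest reply is that the basis is disclosed. The sentence refers to a fall from baseline and to a within-subject SD, so a statistician can see it is a before-after calculation, and section 7.3.1 does plan within-group tests. Sections 1.2 and 1.3 stress safety and right ventricular function, so power to detect a decline to the value the plan calls the risk boundary fits the trial's purpose. That reading is fair, but it is still a within-arm question. The sentence is attached to the primary endpoint, whose objective is comparative, and nothing elsewhere supplies between-arm power.

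Second, the figures are not miscalculated. That stands: the fault is a mismatch between the quoted power and the primary comparison.

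Third, 43% and 61% are conditional. The plan never proposes 0.20 or 0.25 cm as a between-arm difference; these are distances from assumed baselines to a threshold. That also stands, and the numbers should always carry their assumptions. The absence of any between-arm power does not depend on them.

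Fourth, 12 per arm is a minimum, because dropouts are replaced while all randomized subjects are analysed. With an assumed 14 per arm at SD 0.25 cm, rank-sum power is about 51% and 70%, still below the stated figures.

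Finally, this is a small proof-of-concept trial, and section 7.5 does not claim that a null result would exclude benefit. Low power is acceptable in such a trial when it is disclosed. Here the power of a different test stands in its place.

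**Conclusion.** The concern holds. The stated 71% and 88% are correct for a paired t-test of change within one arm of 12. The test is inferred, since none is named, but both figures match it and none of the alternatives tried. They are not the power of the tamoxifen versus placebo comparison, and the plan gives none.

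Under the two assumptions in Step 2 with SD 0.25 cm, the planned rank-sum test would miss a true difference of 0.20 cm about 57% of the time (100 − 43) and one of 0.25 cm about 39% of the time (100 − 61). The shortfall against the stated power is about 28 points (71 − 43) and 27 points (88 − 61). Power stays below the stated figures at every SD from 0.20 to 0.30 cm. The CI half-width of 0.21 cm is slightly larger than the 0.20 cm effect. Randomization, the planned test and its type I error are unaffected. The correction is needed because this is the only sample-size justification for the primary endpoint and it addresses another comparison.

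**What to change.** In section 7.4 and the abstract, replace the power sentence with figures for the between-arm test, stating the assumed SD of change in each arm and the assumed difference in change. The sponsor should choose and justify those values. With the plan's current numbers carried over, the text could read: *With 12 per arm, two-sided 0.05 and an assumed SD of 0.25 cm for the Week 0 to 24 change in each arm, the rank-sum test has about 43% power for a between-arm difference in change of 0.20 cm and about 61% for 0.25 cm; 80% power corresponds to about 0.31 cm.* Adding the expected 95% CI half-width (about 0.21 cm) would suit a proof-of-concept trial.

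If 71% and 88% are kept, label them as power for a within-arm decline and name the paired t-test. The signed-rank test actually planned for within-arm change gives about 67% and 85%.

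In section 7.3.1, state that the between-arm rank-sum test carries the primary claim and that the within-arm signed-rank tests are descriptive.

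The cost is wording in three places and a less favourable stated power. No patients are added and the planned primary test does not change.
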